4.3.3 Analysis of additional research blood

Other blood samples (≤ 25 ml per 4 weeks) may be drawn for research purposes. There will be no genetic or germ line testing unless the patient is reconsented.

4.4 ON STUDY EVALUATION

4.4.1 Prior to Each Cycle the following will be done:

- Staging will be completed prior to each cycle. This will include an interim history and physical examination with documentation of measurable disease, stage, and performance status. Physical examination should record the diameter, in two planes, of the largest palpable nodes in each of the following sites: cervical, axillary, supraclavicular, inguinal, and femoral. Physical examination should record liver and spleen size as determined by measurement below the respective costal margin.
- FACS analysis of the peripheral blood will be done.
- Laboratory evaluation to be done on or within 3 days prior to day 1 are: CBC/diff, acute care panel, hepatic panel, mineral panel, LDH, PT, PTT, urinalysis, fibrinogen, D-dimer, uric acid, amylase, lipase, CK, IgG, IgA, IgM, CRP, ferritin, haptoglobin, Beta-2 microglobulin and SPEP, 24 hour urine.
- ECG, CXR.

4.4.2 Routine Tests done during Each Cycle

4.4.2.1 Days 3, 5

CBC/diff, acute care panel, hepatic panel, mineral panel, LDH, urinalysis, uric acid, CK.

4.4.2.2 Weeks 2 and 3

The following labs will be drawn once during weeks 2 and 3: CBC/diff, acute care panel, hepatic panel, and albumin.

4.4.2.3 Follow-Up

For follow-up studies in patients off-treatment, which will not affect eligibility for enrollment or retreatment, a non-radioactive neutralization assay may be used, under non-CLIA conditions. For additional correlation between the 2 assays, serum samples are saved to enable the new assay to be run with historical samples previously tested using the radioactive CLIA assay.

4.4.3 Other tests that will be done at specific times:

- Bone marrow biopsy will be done 8 weeks after the patient meets clinical criteria for a CR. A bone marrow biopsy may also be done (but is not required) at the time that clinical CR is documented. Research samples at the time of bone marrow aspirate include sodium heparin (green top) tubes for MRD analysis and flow cytometry, and an EDTA tube for PCR (molecular pathology). Research blood samples at the time of a bone marrow will include flow cytometry, DNA and RNA PaxGene tubes for molecular analysis, and 2 serum separator tubes for neutralizing antibodies and soluble tumor markers.
- CT/MRI scan will be done 8 weeks after the patient meets clinical criteria for a CR. A CT/MRI scan may also be done (but is not required) at the time that clinical CR is documented. If no lymph nodes are found prior to enrollment, an ultrasound rather than CT/MRI may be done at the discretion of the PI.

4.5 COST AND COMPENSATION

4.5.1 Costs

NIH does not bill health insurance companies or participants for any research or related clinical care that participants receive at the NIH Clinical Center. If some tests and procedures performed outside the NIH Clinical Center, participants may have to pay for these costs if they are not covered by insurance company. Medicines that are not part of the study treatment will not be provided or paid for by the NIH Clinical Center.

4.5.2 Compensation

Participants will not be compensated on this study.

4.5.3 Reimbursement

The NCI will cover the costs of some expenses associated with protocol participation. Some of these costs may be paid directly by the NIH and some may be reimbursed to the participant/guardian as appropriate. The amount and form of these payments are determined by the NCI Travel and Lodging Reimbursement Policy.

4.6 TOXICITY CRITERIA

CTCAE term (AE description) and grade: The descriptions and grading scales found in the revised NCI Common Terminology Criteria for Adverse Events (CTCAE) version 3.0 will be utilized until December 31, 2010 for AE reporting. CTCAE version 4.0 will be utilized beginning January 1, 2011. All appropriate treatment areas should have access to a copy of the CTCAE version 4.0. A copy of the CTCAE version 4.0 can be downloaded from the CTEP web site (<http://ctep.cancer.gov>).

4.7 RETREATMENT

Patients without evidence of progression and without sufficient neutralizing antibodies will be eligible to receive retreatment cycles of LMB-2 at the same dose with at least 25 days between cycles. Patients will be tested for neutralizing antibodies prior to each cycle. Treatment may not continue for beyond two cycles for a complete response (CR), beyond four cycles for CR with minimal residual disease (MRD), or beyond six cycles for a partial response (PR) or stable disease (SD) without prior FDA approval.

4.8 SUPPORTIVE CARE

- Allergic reaction will be treated acutely with antihistamines (including diphenhydramine, hydroxyzine, & ranitidine), fluids, bronchodilators, and/or epinephrine.
- Nausea and Vomiting: Patients who develop nausea will be treated with a serotonin 5-HT receptor inhibitor for at least 24 hours after their last episode of nausea. Other antiemetics such as prochlorperazine, metoclopramide, or lorazepam may be used in addition if necessary.
- Myalgias: Patients who develop myalgias may be given acetaminophen 650 to 1000 mg every 6 hours until 24 hours after completing the last dose of LMB-2. It may then be given as needed. Patients may receive NSAIDs or opioid analgesics if acetaminophen is inadequate.
- Vascular leak syndrome/Capillary leak syndrome: supportive care may include fluid and electrolyte management, diuresis, albumin, and cardiovascular support.
- Hypotension: Patients will be encouraged to increase oral fluid intake. In addition, for an orthostatic SBP change of >20 mm Hg and an absolute SBP of <100 mm Hg, an IVF bolus may be given as deemed clinically appropriate. Refractory hypotension may require treatment in the intensive care unit with pressors.
- Fever: Patients who develop temperatures >38.0° C may receive scheduled acetaminophen 650 to 1000 mg every 6 hours until 24 hours after completing the last dose of LMB-2. It may then be given as needed.
- Thrombocytopenia should be treated conservatively. In the absence of bleeding or a planned invasive procedure, platelet transfusions should only be given for a platelet count below 10,000. If invasive procedures are planned or the patient develops bleeding, platelet transfusions should be administered in accordance with standard of practice, usually maintaining a platelet count > 50,000/mm³.
- Symptomatic anemia should be treated with appropriate red blood cell support. Transfusion is recommended if the hemoglobin falls below 8g/dL. Recombinant erythropoietin may be also be used.

- Febrile Neutropenia is a life-threatening complication requiring hospitalization and urgent broad-spectrum antibiotics. Hematopoietic growth factors may be used if clinically indicated. Such cases will be evaluated individually to determine the toxicity grade. Neutropenia due to LMB-2 is not expected.
- Central venous access devices such as a temporary internal jugular or subclavian lines, PICC lines, semi-permanent HICKMAN, Groshong catheters, or medi-port implanted devices can all be used in this study. All devices will have nursing supervision and include patient self-care instruction.
- Nutritional assessment and psychological support: Refractory neoplasms are commonly complicated by malnutrition. Patients with weight loss or evidence of wasting syndrome should have a nutritional consult. When necessary, social Work will be proactively involved with these patients' biopsychosocial well-being.

4.9 CRITERIA FOR REMOVAL FROM PROTOCOL THERAPY AND OFF STUDY CRITERIA

Prior to removal from study, effort must be made to have all subjects complete a safety visit approximately 30 days following the last dose of study therapy.

4.9.1 Criteria for removal from protocol therapy

- Progression of disease during active treatment on study protocol.
- Grade III Allergic Reaction and grade II urticaria despite premedication.
- More than 2 dose reductions are required.
- Patient non-compliance or voluntary withdrawal.
- Patient's serum neutralizes $> 75\%$ of the activity of 1 $\mu\text{g}/\text{mL}$ of LMB-2.
- Grade IV toxicity other than hematologic and CPK.
- Grade IV hematologic toxicity lasting > 5 days.
- Grade IV CPK associated with any other DLT or not resolving to $<$ grade II within 2 weeks.

4.10 POST TREATMENT EVALUATION (OFF TREATMENT BUT ON STUDY)

Patients will be taken off treatment when they meet off treatment criteria. Patients who are off treatment due to toxicity will be followed until resolution of their side effects. On- or off-treatment patients who have not had progressive disease will be followed every 3-12 months until they have progressive disease (see Section 12, Study Calendar). Patients who have progressive disease may also need follow-up for other endpoints, including neutralizing antibodies (see Section 12, Study Calendar). Follow-up assessments will be conducted per PI discretion and may be obtained from clinic visits either at NIH or elsewhere.

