5.4.5 Risks from Radiation Exposure

On this study, participants will receive up to 4 CT scans/year. The total radiation dose for research purposes will be approximately 5.2 rem. The risk of getting cancer from the radiation exposure in this study is 0.5% and of getting a fatal cancer is 0.3%.

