12 STUDY CALENDAR

Procedures	Eligibility Evaluation		Every Treatment Cycle										Post-Treatment	
	Prior to Cycle 1	Pre-cycle	Day 1	Day 2	Day 3	Day 4	Day 5	Day 6	Days 7-8	Week 2	Week 3	Week 4	8 weeks after CR ⁶	Every 3-12 months ⁵
Blood sample for CD25 analysis (by FACS)	X	X												X
History (include PS) & physical exam	X	X												
Echocardiogram, stress test	X													
ECG, CXR	X	X												
CT scan of chest/abdomen/pelvis or abdominal MRI ¹	X												X	X
Serum anti-LMB-2 antibody assay, HIV, Hep BsAg & C	X													
Pregnancy test if applicable	X													
Bone Marrow Biopsy	X												X	
Drug administration (LMB-2)			X		X		X							
CBC/diff	X	X			X		X			X	X			X
Acute care panel, hepatic panel, mineral panel	X ³	X			X		X			X ³	X ³			
Total protein	X													
LDH, PT, Beta-2 microglobulin (B2M), SPEP, urinalysis	X													
LDH, urinalysis, uric acid, CK		X			X		X							
Fibrinogen, D-dimer, uric acid, amylase, lipase, IgG, IgA, IgM, CRP, ferritin, haptoglobin, B2M and SPEP		X												
PT, PTT		X												
24 hour Urine for CrCl	X	X												
Pharmacokinetic Studies ²			X		X		X							
Neutralizing antibodies and soluble Tac		X									X ⁴			X ⁷

Abbreviated Title: LMB-2 for HCL

Version date: 02/07/2023

¹ A CT scan (in patients with an abnormal initial scan) will be done routinely after even cycle numbers (2, 4, 6) and will be done at other times if there is clinical evidence that the patient has had a PR, CR, or progressive disease. Ultrasound can replace CT/MRI in the absence of lymph nodes, at the discretion of the PI.

² Refer to Section [4.3](#) for PK collection instructions and schedule.

³ Albumin is collected instead of mineral panel.

⁴ Between Days 17-25.

⁵ Refer to Section [4.10](#).

⁶ Refer to Section [4.4.3](#).

⁷ Only for patients with PD

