13.2 MEASUREMENT OF RESPONSE

Assessment of clinical response will be made according to the guidelines as outlined above. The objective measures of response, such as bone marrow slides and CT scans, will be saved so that responses may be audited. Staging will include a CBC/differential, an interim history and physical examination with documentation of measurable disease, and performance status. Physical examination should record the diameter, in two planes, of the largest palpable nodes in each of the following sites: cervical, axillary, supraclavicular, inguinal, and femoral. Physical examination if relevant can record liver and spleen size as determined by measurement below the respective costal margin. A CT/MRI or U/S (in patients with an abnormal initial scan) will be done routinely after even cycle numbers (2, 4, 6, 8, 10) and will be done at other times if there is clinical evidence that the patient has had a PR, CR, or progressive disease.

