13.3.2 Duration of Response

In patients in CR, the bone marrow biopsy and CT scan should be done at least 4 weeks after the last dose of the last cycle, at 6 month intervals for 2 years after CR, and then at 1 year intervals, and if positive would indicate relapse rather than invalidation of the CR. The duration of PR or CR is measured from the date a confirmed CR or PR begins, until the date that staging studies are no longer consistent with CR or PR. The duration of overall response will be measured from the date that a confirmed response begins, until the date that recurrent or progressive disease is objectively documented.

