15.2 SAMPLE SIZE/ACCRUAL RATE

The primary objective of this trial will be to determine if LMB-2 can produce responses in a reasonable proportion of patients at the current dose and schedule and thus warrant further testing. Considering that patients have not been able to respond well to either cladribine or BL22, an overall response rate of 50% would be reasonable, and < 20% would be considered too low. The trial will be conducted using a Simon two-stage optimal design [\[75\]](#). With alpha=0.10 (the probability of incorrectly accepting a poor agent), and beta=0.10 (the probability of incorrectly rejecting a good agent), we will try to rule out an undesirably low response probability of 20% ($p_0=0.20$) in favor of a level indicative of acceptable activity, 50% ($p_1=0.50$).

Ten evaluable patients will initially be enrolled. If 0-2/10 demonstrate a CR/PR, then accrual will stop and the agent will be considered inactive. If 3+/10 patients have a CR/PR, accrual will continue until a total of 17 patients have been enrolled. If 3-5 of 17 have a CR/PR, this will be considered insufficient activity, and the agent will not be considered worthy of further development. If 6+/17 have a CR/PR, then the agent will be considered active (and at least potentially able to produce a CR/PR level consistent with 50%). In addition, if there are 6+/17 responding patients, up to 8 additional patients overall (maximum 25 evaluable patients overall) will be allowed to be entered into this trial to be enrolled to provide additional data for secondary endpoints. Confidence intervals will be constructed about the observed response proportions based on a two-stage approach [\[76\]](#). Under the null hypothesis ($p_0=0.20$), the probability of early termination of this trial is 0.68.

Duration of response is also important to evaluate in this population. A statistical summary of the duration of response will be reported, along with the fraction of responding patients who achieve a six month response duration, and the corresponding 95% confidence interval. In addition, a Kaplan-Meier curve of response duration will be created to illustrate the pattern associated with this outcome.

Abbreviated Title: LMB-2 for HCL

Version date: 02/07/2023

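### Follow-up every 3-12 months at discretion, with loss of response dated at detection, can bias the six-month response fraction upward, mainly in partial responders off treatment

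*Combined protocol and SAP*

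**What the plan says.** **Endpoint.** Section 15.2 plans a summary of response duration, "along with the fraction of responding patients who achieve a six month response duration, and the corresponding 95% confidence interval", and a Kaplan-Meier curve.

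**Follow-up.** Section 4.10: "On- or off-treatment patients who have not had progressive disease will be followed every 3-12 months until they have progressive disease". It adds: "Follow-up assessments will be conducted per PI discretion and may be obtained from clinic visits either at NIH or elsewhere".

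**End of response.** Section 13.3.2 closes a CR or PR on the date staging no longer fits that category, and closes overall response on the date recurrence or progression is documented. Both are dates of detection. For patients in CR it also sets marrow and CT at least 4 weeks after the last dose, then "at 6 month intervals for 2 years after CR, and then at 1 year intervals". It sets no matching schedule for PR.

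**Calendar.** In Section 12 the 3-12 month column marks the FACS blood sample, CT/MRI and CBC, plus neutralizing antibodies and soluble Tac for patients with progression only. The row "Bone Marrow Biopsy" is marked at eligibility and 8 weeks after CR. History and physical examination are marked at eligibility and before each cycle. Neither row is marked in the 3-12 month column. (This depends on column positions in the table, which should be checked on the laid-out page.)

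**On treatment.** Section 4.4.1 requires staging, with examination and flow cytometry, before every cycle. Section 4.1 sets 28-day cycles, up to six, with further cycles possible after CR.

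**Imaging.** For patients with an abnormal first scan, the Section 12 footnote lists cycles 2, 4 and 6, while Section 13.2 continues to cycles 8 and 10. Section 5.4.5 says: "On this study, participants will receive up to 4 CT scans/year", with about 5.2 rem for research purposes.

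**The concern.** The reported six-month fraction depends partly on when patients happen to be seen. If a response is lost at month 4 and the next assessment is at month 9, the recorded duration is nine months and the patient counts as a six-month responder. That sequence complies fully with the plan. The error goes in one direction only, because detection cannot come before relapse. The planned Kaplan-Meier curve uses the same dates and does not remove it, and the 95% confidence interval does not cover it.

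The exposed group is mainly partial responders who are off treatment before month 6 of response. Patients can reach that state early: Section 4.9.1 stops therapy for neutralizing antibodies, and Section 2.4.2 notes that several phase I responders with HCL could not be effectively retreated. Because CR and PR have different schedules, the two groups may also differ in recorded durability for reasons of observation alone.

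The calendar adds to this. Site staff working from Section 12 would not schedule the marrow that Section 13.3.2 treats as evidence of relapse, or the examination behind the costal-margin and palpable-node criteria in Section 13.1.3.

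**Working it through.** **The plan's own figure.** The documents give no target or expected value for the six-month fraction. The design probability in Section 15.2 reproduces: P(0-2 responses of 10 at p = 0.20) = 0.678, stated as 0.68. The 2/10, 5/17 rule has type I error 0.094 and power 0.904. None of this depends on follow-up after response.

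**Assumptions for the six-month fraction.** Let S(6) be the true fraction. Durations are exponential: S(t) = exp(-λt), with λ = -ln S(6)/6. I use S(6) = 0.50 and 0.70 as assumed values. The third value, 0.89, is 0.5^(6/36), from the 36-month median CR duration for BL22 in Section 2.3.7. That is a different agent and CR only, so it serves as a sensitivity value.

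**Formula.** A responder is recorded as reaching six months if still in response at the last assessment before month 6. If that assessment is at time L (L = 0 if there is none), the recorded fraction is the average of S(L).

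With no on-treatment staging after onset and randomly timed visits:

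- 3-monthly, L uniform on 3 to 6: [S(3) - S(6)]/(3λ). For 0.50: (0.707 - 0.500)/0.3466 = 0.60.
- 6-monthly, L uniform on 0 to 6: [1 - S(6)]/(6λ). For 0.50: 0.500/0.6931 = 0.72.
- 12-monthly, half have no visit before month 6: 0.5 + 0.5 × 0.721 = 0.86.

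| True S(6) | 3-monthly | 6-monthly | 12-monthly |
|---|---|---|---|
| 0.50 | 0.60 | 0.72 | 0.86 |
| 0.70 | 0.77 | 0.84 | 0.92 |
| 0.89 | 0.92 | 0.94 | 0.97 |

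**Effect of pre-cycle staging.** Assume monthly staging for the first months after onset, then the random schedule. For a true 0.50:

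| Staged monthly after onset | 3-monthly | 6-monthly | 12-monthly |
|---|---|---|---|
| 3 months | 0.60 | 0.65 | 0.68 |
| 5 months | 0.55 | 0.56 | 0.56 |

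For a true 0.70, five months of staging gives 0.74 for all three intervals. Five months is close to the most that six cycles can supply. If response is first seen before cycle 2, the last pre-cycle staging (before cycle 6) is 4 × 28 = 112 days later, about 3.7 months. A scan at the end of cycle 6 makes it 140 days, about 4.6 months.

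**Effect of a month-6 visit.** Take visits every 3 months from onset and a true 0.50. If a relapse found at month 6 counts as failure, the recorded fraction is 0.50. If it counts as a six-month response, the fraction is S(3) = 0.71. The plan does not say which applies.

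**Sampling error.** Half of 25 patients is about 12 responders. The exact 95% interval is 0.21 to 0.79 for 6/12 and 0.35 to 0.90 for 8/12.

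**Imaging count, first year, abnormal first scan.** Baseline plus cycles 2, 4 and 6 makes 4 scans by about week 24. Adding cycles 8 and 10 makes 6 by about week 40, and one scan after CR makes 7. Section 5.4.5 allows 4, or 5.2/4 = 1.3 rem each.

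**The case against.** The plan has real safeguards. Patients on treatment are staged about monthly. Complete responders have a work-up 8 weeks after clinical CR (Section 4.4.3) and marrow and CT every six months for two years. The follow-up column keeps flow cytometry, CBC and CT/MRI, which cover most ways of losing a response. The endpoint is descriptive, and with about 12 responders its interval is wide. All of this stands, and it confines the problem largely to partial responders off treatment. A wide interval still does not correct a one-sided error.

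Three stronger readings are tempting, and the documents do not support them.

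- A reader might infer that the six-month fraction cannot be measured. It can, wherever staging or a visit falls near month 6; the plan only fails to ensure this.
- A reader might infer that a true 50% would be reported as 71% or 100%. The 71% needs a relapse found at month 6 to count as success. The 100% needs no assessment at all before month 12, which pre-cycle staging and the CR schedule largely rule out. Both are upper cases under an assumed six-month median.
- A reader might infer that the radiation figure is understated, at 7.8 rem (6 × 1.3) or 9.1 rem (7 × 1.3). Section 5.4.5 counts research dose only. Section 12 permits MRI, or ultrasound when there are no nodes, and Section 13.2 likewise names CT/MRI or ultrasound. Cycles 8 and 10 arise only with treatment beyond six cycles. Baseline plus cycles 2, 4 and 6 matches the stated four scans. What remains is that the sections list different schedules and do not say which scans count.

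**Conclusion.** The point holds as a limited upward bias in a secondary estimate, together with schedules that conflict. With random visit timing off treatment and no staging after onset, the overstatement is 0.10 to 0.36 for a true 0.50 and about 0.03 to 0.08 for a true 0.89, depending on the interval chosen. It falls to about 0.05 or 0.06 for a true 0.50 with five months of monthly staging, and to near zero with a month-6 visit at which relapse counts as failure. The true fraction, the exponential form and the visit timing are assumptions. The direction needs none of them, only detection dating and gaps that may span month 6.

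The conflict of Section 12 with Section 13.3.2 (marrow) and with the progression criteria (examination) needs no modelling. The two-stage response-rate decision is unaffected. The change is worth making but does not threaten the trial's main conclusion.

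**What to change.** 1. Require a response assessment (CBC, flow cytometry and examination, done locally if convenient) at 6 months from response onset for every responder, PR included. This fits within the existing 3-12 month range.
2. Align Sections 4.10 and 12 with the marrow and CT schedule in Section 13.3.2, and add history and physical examination to the follow-up column.
3. In Section 15.2, count a six-month response only when there is an in-response assessment at or after 6 months. Censor a responder without one at the last in-response assessment, unless loss of response was documented before month 6. Where loss is first found after a gap spanning month 6, carry it as interval-censored in a sensitivity analysis, or date it just after the last in-response assessment.
4. Reconcile the imaging lists in Sections 12 and 13.2 with Section 5.4.5, stating which scans are research CTs and where MRI or ultrasound applies.

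The cost is wording in four or five sections, a few extra local assessments in responders, and possibly a lower reported six-month fraction.
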